6.2.4 Power Estimation

For the primary efficacy endpoint of change in Villalta score at 30 days from Baseline, study success will be defined by $\geq 50\%$ of the evaluable DVT segments achieving at least a 4 point reduction. Assuming the true underlying proportion of such segments to be 55%, the probability for observing a $\geq 50\%$ success proportion in a study with 70 evaluable independent segments is 0.83. On the other hand, should true underlying success proportion be $<40\%$, e.g. 39%, the probability for observing a $\geq 50\%$ success proportion in 70 independent segments is ≤ 0.04 .

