3.1.1 Primary Clinical Efficacy Endpoint

Clinical efficacy will be evaluated using the Villalta score at Baseline compared to 30 days Post-EkoSonic® Study Treatment Procedure. Study success will be defined by ≥50% of the efficacy evaluable limbs achieving at least a 4 point reduction.

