6.2. Statistical Analysis Plan

6.2.1 General Methodology

For baseline demographics and subject characteristics, continuous measures will be summarized as mean, standard deviation, median, minimum and maximum. Categorical data will be summarized as frequencies and percentages for each data category. As appropriate, characteristics of affected segments may be similarly summarized.

For segment specific efficacy endpoints of interest, the analysis unit will be treated segment as opposed to subject. That is, assuming no missing data, subjects with bilateral DVTs will have two segments for analysis. Efficacy results will be summarized for the Efficacy Segment Set at each measurement time point. For changes from baseline at follow-up time points, continuous measures will be summarized as mean, standard deviation, median, minimum, maximum. Categorical outcomes will be summarized in two-way tables. All statistical analyses will take into account the repeated measures nature of multiple segments per subject. With subject as a random effect, the SAS GLIMMIX procedure will generally be used to evaluate the statistical significance for changes from baseline.

Analysis for subject specific efficacy measures such as SF-36 will be performed on the Evaluable Subject Set with subject as the analysis unit. Statistical significance for changes from baseline will be assessed by t-test or a nonparametric test appropriate for the data distribution.

Further analysis details will be described in the Statistical Analysis Plan.

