6.2.5 Interim Clinical Efficacy Futility Analysis

At the time of November 2016 administrative change to the protocol, an interim futility analysis had been performed on the primary clinical efficacy endpoint. The futility stopping criterion was not met and the study continued. It was pre-specified that when data for the primary efficacy endpoint (i.e. change in Villalta score from Baseline to 30 day Post-EkoSonic® Treatment) are available for 35 evaluable subjects segments, an interim futility analysis will be conducted. If 14 or fewer of the 35 segments have achieved a ≥ 4 point reduction for an interim success rate of 40% (1-sided 95% confidence upper limit of 53.9%), early trial termination would be considered due to futility. Should the true success rate be 40% as observed in the interim, the chance of reaching a 50% success rate at full enrollment of 70 evaluable subjects segments (i.e. 21 or more segments in the remaining 35 segments), is ≤ 0.013 . Should the underlying success rate be 53.9%, i.e. the 95% confidence upper limit of the interim success rate, the chance of observing a 50% success rate at full enrollment is still only 0.29. Therefore it is highly unlikely that the trial would meet its efficacy success criterion at full enrollment and early trial termination would be recommended. The negative impact of this futility analysis on the study's power is <0.05 . The study would not stop early due to favorable interim efficacy results; therefore this interim analysis will not incur an alpha cost due to potentially false positive findings.

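### The power of 0.83 and false-success bound of 0.04 in section 6.2.4 hold only for 70 independent limbs, while section 6.2.1 counts both limbs of bilateral subjects as repeated measures

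*Protocol*

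**What the plan says.** Section 3.1.1 sets clinical success as half or more "of the efficacy evaluable limbs achieving at least a 4 point reduction". Section 6.2.2 repeats this for segments. The rule is a raw proportion, and no test or confidence limit enters it.

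Section 6.2.4 gives two operating characteristics for that rule. For power, it begins "Assuming the true underlying proportion of such segments to be 55" percent and concludes "success proportion in a study with 70 evaluable independent segments is 0.83". For true rates under 40%, with 39% as its example, the "success proportion in 70 independent segments is ≤ 0.04".

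Section 6.2.1 describes the units differently. It states that "the analysis unit will be treated segment as opposed to subject", that "subjects with bilateral DVTs will have two segments for analysis" if nothing is missing, and that "All statistical analyses will take into account the repeated measures nature of multiple segments per subject", with subject as a random effect.

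Section 6.2.5 counts the planned size in segments: "at full enrollment of 70 evaluable subjects segments". The synopsis and section 4.0 allow up to 200 evaluable subjects, some of them bilateral. The protocol gives no expected number of bilateral subjects and no within-subject correlation.

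**The concern.** Section 6.2.4 assumes independence for units that section 6.2.1 treats as dependent within a subject. Two limbs of one person share the anticoagulation and exercise regimen (4.2.5, 8.9), preferably the same assessor (4.0, 8.7) and the same self-reporter for the self-rated items (8.7). A positive correlation between their outcomes is therefore plausible.

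Positive correlation leaves the expected proportion unchanged and widens its spread. The success threshold lies below the assumed true rate of 55% and above the unfavourable rate of 39%, so a wider spread lowers power and raises the chance of a false success. The random effect in 6.2.1 cannot repair this, because it does not alter whether 35 of 70 limbs responded. In a single-arm study with a raw-proportion rule, 6.2.4 is the protocol's only general statement of how often an inadequate treatment would pass. A reader will rely on it.

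**Working it through.** **Inputs from the protocol.** Limbs n = 70 (6.2.4, 6.2.5). Success if at least 50% respond, that is 35 or more of 70 (3.1.1, 6.2.2). True rates p = 0.55 and 0.39 (6.2.4).

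**Inputs assumed, because the protocol does not give them.** The number b of bilateral subjects among the 70 limbs (so 70 − b subjects) and the within-subject correlation r. Both limbs of a pair have the same success rate p.

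**Step 1: the protocol's own figures.** With independent limbs, X ~ Binomial(70, p):
- P(X ≥ 35 | p = 0.55) = 0.8318, stated as 0.83.
- P(X ≥ 35 | p = 0.39) = 0.0400 (0.04003 to five places), stated as at most 0.04.

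Both reproduce. The second has no margin.

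**Step 2: allow for pairs.** For a bilateral subject:
- P(both succeed) = p² + r·p(1 − p)
- P(exactly one succeeds) = 2p(1 − p)(1 − r)
- P(neither succeeds) = (1 − p)² + r·p(1 − p)

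At p = 0.39 and r = 0.5 these are 0.271, 0.238 and 0.491. The total is the exact convolution of b such pairs with 70 − 2b single limbs. The variance of the count is multiplied by 1 + 2b·r/70. For b = 10, r = 0.5 this is 1 + 10/70 = 1.14.

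**Step 3: results at 70 limbs.**

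| Bilateral subjects / all subjects | r | Power at 55% | False success at 39% |
|---|---|---|---|
| any | 0 | 0.832 | 0.040 |
| 1 / 69 | 0.5 | 0.830 | 0.041 |
| 4 / 66 | 0.3 | 0.828 | 0.043 |
| 5 / 65 | 0.5 | 0.823 | 0.046 |
| 7 / 63 | 0.3 | 0.825 | 0.045 |
| 10 / 60 | 0.5 | 0.816 | 0.051 |
| 14 / 56 | 0.5 | 0.810 | 0.055 |
| 20 / 50 | 0.8 | 0.787 | 0.074 |

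At r = 0.5, false success first rounds to 0.05 at 5 pairs. Power is more than two points below 0.83 only from 14 pairs.

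**Step 4: the wording about rates under 40%, apart from clustering.** With 70 independent limbs, P(X ≥ 35 | p = 0.40) = 0.0574, and just below 40% it is about 0.057. The bound of 0.04 therefore fits the 39% example but not the whole range it is attached to. With 10 pairs at r = 0.5, the figure at 40% becomes 0.070. Of the rise from 0.040 to 0.070, 0.017 comes from moving the true rate (0.057 − 0.040) and 0.013 from clustering (0.070 − 0.057).

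**Step 5: dependence on limb number.** With 200 limbs, all in bilateral pairs and r = 1 (equivalent to 100 independent units), power is 0.865 and false success at 39% is 0.016. With 100 limbs, 28 pairs and r = 0.8, false success is 0.038. The shortfall belongs to the stated 70 limbs.

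**The case against.** The strongest reply is that section 6.2.4 says openly, both times, that its segments are independent, and its arithmetic is right under that condition. This stands: the point concerns an unsupported planning assumption, not a calculation error.

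A reader might infer that the design cannot deliver either figure, or that the false-success rate nearly doubles. The documents do not support either statement. The size depends on a bilateral count and a correlation that they do not give, and 0.074 needs 40% of subjects to be bilateral with r = 0.8. With 4 pairs at r = 0.3 the results still round to 0.83 and 0.04. Section 4.2.1 also has the limbs treated at least 30 days apart and evaluated separately through 90 days, so a high correlation cannot be presumed.

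It can also be said that the study may analyse far more than 70 limbs, in which case both figures could be better than stated. That is correct for numbers near the 200-subject cap. But 6.2.4 and 6.2.5 present 70 as the basis and as full enrollment, and the protocol does not reconcile the two numbers.

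Finally, 6.2.1 already commits to analyses that respect repeated limbs and leaves details to the statistical analysis plan. The lack of a clustered interval is therefore no defect here. That commitment still does not change the operating characteristics of a raw-proportion rule.

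**Conclusion.** The point holds in a limited form and is minor. The figures in 6.2.4 are valid under independence, a condition that 6.2.1 does not accept for bilateral subjects. At 70 limbs, every positive correlation examined moves both figures the wrong way. Power loses about one to two points in moderate scenarios. The false-success bound is the weaker statement: it is strictly exceeded from the first correlated pair (0.041) and reaches about 0.05 with 10 pairs at r = 0.5. These sizes rest on assumed bilateral counts and correlations and on a common success rate for both limbs of a pair.

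Independently of clustering, the 0.04 bound does not hold for all true rates under 40%, since the probability just below 40% is about 0.057 with independent limbs.

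**What to change.** Restate 6.2.4 with the expected or actual number of bilateral subjects and a range of within-subject correlation, giving power at 55% and false success at 39% across that range. Compute these at the limb number that will be analysed, and reconcile the 70 in 6.2.4 and 6.2.5 with the cap of 200 subjects in the synopsis and 4.0. Tie the 0.04 figure to 39% alone, or quote about 0.057 for rates just under 40%.

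Add a sensitivity proportion using one limb per subject, the first treated. It can be placed in the statistical analysis plan.

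The cost is a few recalculated figures, one additional analysis line, and slightly less favourable stated properties if 70 limbs remains the basis.

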6.2.2 Efficacy

Efficacy analyses will be performed on the Efficacy Segment Set or Efficacy Subject Set as appropriate for the nature of the data.

Primary Clinical Efficacy Analysis:

The 30 day Villalta score change from Baseline will be analyzed as a binary variable for a segment's status as having achieved a ≥ 4 point reduction or not. Study success will be defined by $\geq 50\%$ of the efficacy evaluable segments achieving at least a 4 point reduction. In addition, as a continuous measure, change in Villalta score from Baseline to 30 day Post-EkoSonic® Treatment will also be summarized and analyzed as described above in 6.2.1 General Methodology.

Primary Technical Efficacy Analysis:

The change in blood flow calculated by time to washout in the affected segment from Baseline and Post-EkoSonic® Treatment will be analyzed as a continuous measure. A statistically significant (2-sided $p < 0.05$) improvement in flow rate, i.e. reduction in time to washout, will be considered a success for the study.

Secondary Efficacy Analyses:

For all secondary efficacy endpoints described in Section 3.2.1, i.e. VVI score change from Pre- EkoSonic® Treatment to Post-Treatment, Villalta score change from Baseline to 90, 180, and 365 days, re-occlusion rate up to 365 days, change from Baseline to all follow-up time points for SF-36 QOL and PCS component scores, CEAP classification, and VCSS, occurrences of symptomatic PTS-induced admission to emergency room or unplanned visit

to physician office or hospitalization from post EkoSonic® Treatment up to 365 days thereafter, time from starting initial thrombolytic infusion to discharge from hospital, analyses will be performed as described above in 6.2.1 General Methodology. For symptomatic PTS-induced healthcare utilization, time to event analyses will be performed for days from EkoSonic® Treatment to first occurrence for each of (a) admission to emergency room, (b) unplanned visit to physician office, and (c) hospitalization.

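### The 0.04 false-success probability in Protocol Section 6.2.4 is right at a true rate of 39% but is not a bound for every rate below 40%

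*Protocol*

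**What the plan says.** Section 6.2.4 of the protocol evaluates the primary clinical success rule, under which the study succeeds if 50% or more of the evaluable segments improve by 4 or more Villalta points at 30 days. It gives two operating characteristics.

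- **Favourable case.** "Assuming the true underlying proportion of such segments to be 55"%, the chance of meeting the rule "in a study with 70 evaluable independent segments is 0.83".
- **Unfavourable case.** "On the other hand, should true underlying success proportion be" below 40%, "e.g. 39%, the probability for observing a" result of 50% or more is at most 0.04. The setting is the same: "success proportion in 70 independent segments is" the phrase that leads into that figure.

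Section 6.2.2 repeats the success rule ("Study success will be defined by" an observed proportion of 50% or more). Neither section gives a null proportion or a significance level for this endpoint. Section 6.2.5 describes a futility look at 35 segments, with early termination considered at 14 or fewer successes.

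**The concern.** The condition in the unfavourable case is a range, 39% is offered as one example from it, and the conclusion is an inequality. Read that way, the sentence says that no true rate below 40% gives more than a 0.04 chance of declaring success. The probability rises with the true rate, so the bound over the range is set at its upper end, just under 40%, and not at 39%. The value at the example appears to have been attached to the whole range.

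The primary clinical endpoint is judged on the observed proportion alone. This sentence is therefore the only place where the protocol says, without conditioning on interim data, how often an inadequate true rate would pass. A reader who takes 40% as the edge of the unacceptable range would carry away a figure that is somewhat too favourable.

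**Working it through.** **Inputs**, all from the protocol:

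- n = 70 independent segments (Section 6.2.4).
- Success means 50% or more, so X ≥ 35, and exactly 35 counts (Sections 3.1.1, 6.2.2 and 6.2.4).
- True rates: 55% for power; below 40%, for example 39%, for false success (Section 6.2.4).

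**Formula.** P(X ≥ 35 | 70, p) = Σ from k = 35 to 70 of C(70, k) p^k (1 − p)^(70 − k).

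**Step 1: reproduce the plan's own figures.**

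| Quantity | Stated | Exact binomial |
|---|---|---|
| P(X ≥ 35 of 70), p = 0.55 | 0.83 | 0.8318 |
| P(X ≥ 35 of 70), p = 0.39 | ≤ 0.04 | 0.0400 |
| P(X ≥ 21 of 35), p = 0.40 (Section 6.2.5) | ≤ 0.013 | 0.0133 |
| P(X ≥ 21 of 35), p = 0.539 (Section 6.2.5) | 0.29 | 0.291 |

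All four agree to the precision given, so the exact binomial tail is consistent with the plan's method.

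**Step 2: apply the same formula across the stated range.**

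| True rate | P(X ≥ 35 of 70) |
|---|---|
| 38% | 0.0271 |
| 39% | 0.0400 |
| 39.5% | 0.0481 |
| 39.9% | 0.0555 |
| 39.99% | 0.0572 |
| limit at 40% | 0.0574 |

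The value rounds to 0.04 up to a true rate of about 39.3%. The largest gap is 0.0574 − 0.0400 = 0.0174, approached but not reached for rates below 40%.

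**Step 3: see whether another calculation would make the bound true.**

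- *Normal approximation with continuity correction.* At 40% the mean is 70 × 0.40 = 28 and the SD is √(70 × 0.40 × 0.60) = √16.8 = 4.10. Then z = (34.5 − 28)/4.10 = 1.59, with a tail of 0.056. The bound still fails.
- *Normal approximation without correction.* This gives 0.044 at 40%, still above 0.04, and 0.800 at 55%, which does not match 0.83.
- *Success only above 50% (X ≥ 36).* This gives 0.035 at 40%, which would satisfy the bound. But it gives 0.765 at 55%, contradicting the stated 0.83, and it departs from the written rule, which counts exactly 50% as success.
- *Futility rule treated as binding (stop at 14 or fewer of 35).* This gives 0.038 at 39% and about 0.054 at 39.99%. The bound still fails.

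No calculation that reproduces 0.83 and follows the written rule makes 0.04 hold up to 40%.

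**The case against.** The best defence is that the 0.04 belongs to the 39% example. Section 6.2.4 works in whole percentage points (55%, 40%, 39%), and in those units below 40% means 39% or less, where the figure holds to two decimals. Section 6.2.5 also puts a less-than-or-equal sign on a probability at a single true rate of 40% (0.013, exact 0.0133), so in this protocol the sign can accompany a rounded point value. This shows how the sentence probably arose, and that the number was not miscalculated. It does not remove the problem: the condition is still written as a range and 39% as an example of it, so the sentence as it stands claims more than the figure supports.

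A second defence is that the study may be larger than 70 segments, since Section 4.0 allows up to 200 evaluable subjects. With 200 independent segments, P(X ≥ 100) at a true 40% is 0.0026, and 0.04 would hold over the whole range. That is correct as an illustration, but 200 is a ceiling and the sentence is explicitly about 70.

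Two stronger readings are tempting and should be resisted.

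- A reader might infer that the design breaches a 5% error limit, because the probability passes 0.05 at a true rate of about 39.6%. The protocol sets no such limit for this rule; the 0.05 level in Section 6.2.2 belongs to the technical endpoint.
- A reader might infer that this is the only operating characteristic given for the primary clinical decision. Section 6.2.5 adds chances of success following a poor interim result, a limit on the loss of power and a remark on alpha. What is unique to Section 6.2.4 is the unconditional false-success probability.

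**Conclusion.** The point holds as a minor misstatement of range. The 0.04 is correct at 39%; over all true rates below 40% the correct bound is 0.057, a difference of at most 0.017. The result rests on 70 independent segments and success at 35 or more, both taken from the protocol. The sample size, the 0.83 power, the 50% success rule and the 14-of-35 futility rule are unaffected.

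**What to change.** Change the sentence in Section 6.2.4 in one of two ways:

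- narrow the range: *at a true proportion of 39% or less, the probability is at most 0.04*; or
- keep the range and correct the figure: *for a true proportion below 40%, the probability is less than 0.058 (0.040 at 39%)*.

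Either is correct to the precision shown. The second is more informative, because Section 6.2.5 also uses 40% as a reference rate. The cost is one sentence: the first option gives up the claim for rates between 39% and 40%, and the second shows a slightly less favourable figure. Neither needs new data, a new calculation of size or a change to any decision rule.

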6.2.5 Interim Clinical Efficacy Futility Analysis

At the time of November 2016 administrative change to the protocol, an interim futility analysis had been performed on the primary clinical efficacy endpoint. The futility stopping criterion was not met and the study continued. It was pre-specified that when data for the primary efficacy endpoint (i.e. change in Villalta score from Baseline to 30 day Post-EkoSonic® Treatment) are available for 35 evaluable subjects segments, an interim futility analysis will be conducted. If 14 or fewer of the 35 segments have achieved a ≥ 4 point reduction for an interim success rate of 40% (1-sided 95% confidence upper limit of 53.9%), early trial termination would be considered due to futility. Should the true success rate be 40% as observed in the interim, the chance of reaching a 50% success rate at full enrollment of 70 evaluable subjects segments (i.e. 21 or more segments in the remaining 35 segments), is ≤ 0.013 . Should the underlying success rate be 53.9%, i.e. the 95% confidence upper limit of the interim success rate, the chance of observing a 50% success rate at full enrollment is still only 0.29. Therefore it is highly unlikely that the trial would meet its efficacy success criterion at full enrollment and early trial termination would be recommended. The negative impact of this futility analysis on the study's power is <0.05 . The study would not stop early due to favorable interim efficacy results; therefore this interim analysis will not incur an alpha cost due to potentially false positive findings.

7.0 RISK ANALYSIS

7.1 Description and Analysis of Risks

The risks that are associated with use of the EkoSonic® Endovascular System are expected to be the same as the risks associated with the placement of any catheter into the venous system including vessel injury such as dissection, perforation, or rupture and are listed in the IFU Appendix A. Potential risks associated with thrombolytic drugs are listed in the package insert for alteplase (Appendix B). Potential risks for subjects undergoing the procedure are listed in the following table.

Table 1 Anticipated Adverse Events During EkoSonic® Treatment

Adverse Event	Definition
Amputation	Surgical removal of any portion of the involved leg, foot or toes.
Arrhythmia	Irregularity or loss of rhythm of the heartbeat requiring treatment with drugs, cardioversion, or pacemaker.
Bleeding – Access site	Clinically significant bleeding at the catheter access site
Bleeding - Other	Clinically significant bleeding at any site other than the access site
Congestive Heart Failure	Development of an acute episode of or exacerbation of existing low cardiac output accompanied by distal and/or pulmonary edema requiring tracheal intubation or Intensive Care Unit care.
Contrast Reaction	Documented reaction directly attributed to contrast medium used during the angiography or venography.
Death	All deaths should be reported regardless of cause
DVT – Recurrent, same limb	A new episode of DVT in the study limb. If subject was discharged, any returns for DVT symptoms will be considered recurrent.
DVT – Recurrent, other	A new episode of DVT in a non-study limb.
Device Issue	Any device operation / malfunction that results in a negative clinical occurrence for the subject. Failure to lyse or automatic shut off as outlined in the IFU will not be considered a Device Issue.
Distal Embolization	Filling defect with an abrupt 'cutoff' in one of the peripheral vessels distal to the site of treatment.
Dyspnea	Labored or difficult breathing
Embolism	Blockage of a vessel by dislodged thrombus confirmed by angiography
Hematoma - Access site	Clinically significant localized collection of blood at catheter access site
Hematoma - Other	Clinically significant localized collection of blood at any site other than access site
Infection - Systemic	Systemic infection as indicated by increase in white blood cell count sufficient to warrant antibiotic therapy.
Infection - Wound	Wound drainage or erythema of the access site documented by positive culture and requiring drainage, debridement, and/or antibiotic therapy.

Adverse Event	Definition
Inflammation - Wound	Prolonged or abnormal pain, redness, and swelling at the access site.
Intracranial Hemorrhage	Intracranial hemorrhage related to a decline in neurological status and consistent with new or worsening symptoms in the judgment of the Investigator.
Medication Reaction	Documented reaction directly attributed to prescribed medication.
Myocardial Infarction	Significant elevation of CPK-MB (based on local norms), appearance of new significant Q wave or loss of R waves.
Neurovascular	Documented complication of both the nervous and vascular systems of the involved limb.
PE - Proved	Intravascular migration of a venous thrombus to the pulmonary arterial circulation proved by a positive pulmonary angiogram, a positive helical CT scan, a high-probability ventilation-perfusion scan or autopsy.
PE - Suspected	Intravascular migration of a venous thrombus to the pulmonary arterial circulation suspected based on clinical symptoms / signs but where no diagnosis has been made by imaging or autopsy.
Renal failure	Creatinine level increase >30% of the preoperative level or requiring dialysis.
Respiratory Failure	The need for mechanical ventilation or the need for intubation and ventilator support any time during the study (unless the subject was ventilator dependent when he/she entered the study).
Stroke	Development of a new permanent neurologic deficit or exacerbation of a prior deficit as determined by CT/MRI Scan and/or clinical exam
Thrombosis, vascular	A new or recurrent occlusion
Transient ischemic attack	Development of a new transient neurologic deficit as determined by CT/MRI Scan and/or clinical exam that occurs
Vascular complication	Any complication of the treated vessel including dissection, perforation, spasm, pseudoaneurysm, occlusion, or arteriovenous fistula (AV fistula).
Other	Complications not specifically listed, which are determined to be associated with the device, the procedure or condition.

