3.2.1 Secondary Clinical Efficacy Endpoints

1. Occlusive material burden using the Venous Volumetric Index (VVI) Score¹¹, measured at Baseline and Post-EkoSonic® Study Treatment Procedure, both as a continuous measure and as a binary variable for achievement of a ≥ 5 point reduction from Baseline to Post-Procedure.
2. Change in Villalta score from Baseline to 90 days, 180 days, and 365 days Post-EkoSonic® Study Treatment Procedure, both as a continuous measure and as a binary variable for having achieved a ≥ 4 point reduction from Baseline.
3. Absence of re-occlusion at 365 days of the treated segment, as documented by duplex imaging.
4. Change in SF-36 Quality of Life (QoL) and Physical Component Summary (PCS), CEAP classification, VEINES-QOL, and VCSS from Baseline to 30, 90, 180 and 365 days Post-EkoSonic® Study Treatment Procedure.
5. Symptomatic PTS-induced admission to emergency room or unplanned visit to physician office or hospitalization from Post-EkoSonic® Study Treatment Procedure up to 365 days thereafter
6. Time from starting initial thrombolytic infusion to discharge from hospital

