4.1 Study Population

4.1.1 Inclusion Criteria

Subjects must meet the following criteria to be eligible for participation in this clinical trial:

1. Male or female ≥ 18 years of age and ≤ 75 years of age.
2. Proximal DVT (iliac vein, common femoral vein, deep femoral vein, femoral vein) that was objectively diagnosed with duplex imaging and/or venography ≥ 6 months prior to study screening.
3. Persistent chronic DVT causing restrictive flow, as confirmed by imaging, within 60 days prior to the study procedure.
4. Villalta score ≥ 8 for the affected limb within 30 days prior to the study procedure.
5. Medically eligible for treatment with thrombolytic drugs (see alteplase package insert in Appendix B).
6. Informed of the nature of the trial, is willing and has provided written, informed consent as approved by the Institutional Review Board/Ethics Committee (IRB/EC) of the respective investigational site.

7. Failed a minimum of 3 consecutive months of conservative treatment (therapeutic anticoagulation and compression stockings) according to the completed Adherence to Conservative Treatment Form.
8. Agrees to comply with specified follow-up evaluations and to return to the same investigational site where the procedure was performed.

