4.2.5 Discharge

The subject shall be discharged with prescriptions for enoxaparin (1 mg/kg bid for 90 days) and a pair of 30 to 40 mm Hg ECS. If necessary, enoxaparin may be converted to an oral anticoagulant after 30 days (e.g. 20 mg rivaroxaban daily). Treatment with the ECS and oral anticoagulation should continue for the duration of the study.

If limb swelling and discomfort is too great for standard ECS use, leg wraps, leg elevation, and pumps can be used to reduce the swelling and pain and allow for earlier ECS use. One may also consider using 20-30 mmHg ECS if necessary. The subject shall be encouraged to ambulate and exercise early and often, as tolerated.

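### Table 1 classes a symptomatic return after discharge as recurrent DVT of the study limb with no objective confirmation, so PTS-type symptoms without new thrombus can be recorded as recurrence

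*Protocol*

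**What the plan says.** The Table 1 row for recurrent DVT in the same limb has two sentences. The first gives the concept: "A new episode of DVT in the study limb". The second gives a rule for subjects who have left hospital: "If subject was discharged, any returns for DVT symptoms will be considered recurrent". The protocol does not define DVT symptoms, and nowhere adds an imaging requirement for this term. The next row, for recurrent DVT in a non-study limb, has no symptom sentence.

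Other parts of the protocol that bear on this:

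- **Population (4.1.1).** Entry requires "Villalta score ≥ 8 for the affected limb within 30 days prior to the study procedure" and "Persistent chronic DVT causing restrictive flow, as confirmed by imaging, within 60 days prior to the study procedure".
- **After discharge (4.2.5).** The protocol provides for the case "If limb swelling and discomfort is too great for standard ECS use".
- **Secondary endpoint 5 (3.2.1).** It counts "Symptomatic PTS-induced admission to emergency room or unplanned visit to physician office or hospitalization" up to 365 days.
- **PE in the same table.** Proved and suspected PE are separate rows. The suspected row is for PE "suspected based on clinical symptoms / signs but where no diagnosis has been made by imaging or autopsy".

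**The concern.** The second sentence is triggered by symptoms, not by a finding. In a population without leg disease that might be a tolerable shorthand. Here every subject already has PTS and a chronically obstructed vein in the study limb, so limb symptoms alone do not separate new thrombosis from the condition under treatment. The protocol gives no rule for telling a return for DVT symptoms from a PTS-induced return.

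What is at stake is how the AE tables for recurrent DVT and VTE can be read. Section 3.1 makes safety part of the primary objective, and the trial has a single arm, so no control group is coded under the same rule. A reader would take the recurrent DVT line as a count of new thrombosis, when part of it could be symptom visits.

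**Working it through.** No arithmetic applies: the protocol states neither an expected rate of recurrent DVT nor an expected rate of symptom-driven returns. The check is textual. Take one visit and run it through each rule.

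**The visit.** A discharged subject comes back with swelling and pain in the study limb, no worse than at baseline. Duplex shows no new thrombus. The subject is not admitted.

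| Rule | What it does with this visit |
|---|---|
| Table 1, same-limb row, second sentence | If the complaint is taken as DVT symptoms: recurrent DVT |
| 5.5, pre-existing conditions | Not an AE, because the condition has not worsened significantly or unexpectedly |
| 5.10, reporting guidelines | A known diagnosis is recorded in place of symptoms; here that would be PTS, not new DVT |
| 5.8, collection period | If coded as recurrent DVT, it falls among the VTE-related events still collected after Day 30 |
| 5.14, safety monitor | Not adjudicated: the remit is serious events and bleeding |
| 6.2.3, safety analysis | Whatever code was entered is mapped and counted as a subject with that event |
| 3.2.1 item 5 | Counts as an unplanned visit if judged PTS-induced |

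Three things follow.

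1. Table 1 and sections 5.5 and 5.10 give different answers for the same visit, and nothing says which prevails. Two sites can each follow the protocol and code it differently.
2. No later step corrects a non-serious case. It passes from site entry to the table without adjudication.
3. The row is out of line with its neighbours. PE without imaging has its own row, the embolism row requires angiography, and the non-study-limb DVT row has no symptom rule. Only the study limb has a category that symptoms alone can fill.

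**Reach.** The primary Villalta and washout endpoints do not use the row. Nor do the secondary endpoints; re-occlusion is "Absence of re-occlusion at 365 days of the treated segment, as documented by duplex imaging". The named safety endpoints in 3.3 are major bleeding and symptomatic PE, and 6.2.3 adds death. Only the general AE tabulation is exposed.

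**The case against.** The best defence is that Table 1 does not govern coding. It sits in the risk analysis, its title concerns events during treatment, and sections 5 and 6 do not refer to it. AE reporting is set out in section 5, where 5.5 and 5.10 would keep unchanged PTS symptoms from being coded as DVT. Duplex is scheduled within 24 hours of treatment and at every follow-up visit, so imaging will often inform the diagnosis.

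Part of this stands. It is why the consequence is that such visits can be recorded as recurrences, not that they will be. But the table reads as operative: its death row tells sites what to report, its device row says what does not count, and the disputed sentence itself applies after discharge. Sections 5.5 and 5.10 do not override it; they conflict with it.

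A second defence is that the sentence only labels a post-discharge episode as recurrent rather than as a continuation of the index event. That is plausible, but the sentence speaks of returns for symptoms, not of episodes. If that was the intent, rewording is still needed.

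A third is that over-counting harm is conservative for the device. The direction is right where the sentence is followed. It does not help with coding that differs between sites, or with separating true recurrences from symptom visits.

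A reader might also infer that the row contradicts the duplex re-occlusion endpoint, or that counting a visit both as an AE and under 3.2.1 item 5 is an error. The documents support neither. Re-occlusion concerns the treated segment and the AE row concerns the limb, so new DVT elsewhere in the limb is compatible with a patent segment. An AE table and a utilisation endpoint answer different questions and may share a visit.

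**Conclusion.** The point holds as a defect of definition with limited reach. The same-limb row allows recurrent DVT to be recorded on symptoms alone, in subjects who all have symptomatic PTS and chronic DVT in that limb. It conflicts with sections 5.5 and 5.10 and with the table's own handling of PE, and non-serious cases are not adjudicated.

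The conclusion assumes that sites use Table 1 when classifying events, and that some returns for PTS-type symptoms are taken as DVT symptoms. The text permits both and guarantees neither, so it does not support saying that ordinary PTS symptoms are routinely reported as thrombosis.

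The size of any over-count cannot be derived from the protocol. A multiplier would only restate assumed rates. The 70 in section 6.2.4 would also be the wrong denominator, since it counts evaluable segments whereas AEs are reported on the Safety Subject Set. The exposure is the AE tabulation of recurrent DVT and VTE-related events, and no study success criterion changes.

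**What to change.** In Table 1:

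1. Delete the second sentence of the same-limb row.
2. Define recurrent DVT, for both the same-limb and the other-limb rows, as new thrombus confirmed by duplex or venography.
3. Add a suspected DVT row for symptomatic returns without imaging confirmation, parallel to the suspected PE row.
4. State that a symptomatic return where imaging shows no new thrombus is reported under whichever AE or serious AE term applies by sections 5.3, 5.5 and 5.10, and is also counted under 3.2.1 item 5 if PTS-induced.

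The fourth step should not route such returns to 3.2.1 item 5 alone. That would take significant worsening, or an event leading to admission, out of safety reporting, against sections 5.3 and 5.5.

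The cost is a wording change in Table 1 and in any matching coding instructions, with no new study procedure. The downside is that a true recurrence that was never imaged moves to the suspected row, where it is still reported.
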